6.10. Diagnostic and Laboratory Testing

6.10.1. Microscopy

Thick and thin blood smears will be stained with 2% Giemsa and read by experienced laboratory technologists. Parasite densities will be calculated by counting the number of asexual parasites per 200 leukocytes (or per 500 leukocytes, if the count is <10 asexual parasites/200 leukocytes), assuming a leukocyte count of 8,000/ μ l. A blood smear will be considered negative when the examination of 100 high power fields does not reveal asexual parasites. Gametocytemia will also be determined from thick smears. Thin smears will be used for parasite species identification. For quality control, all slides will be read by a second microscopist and a third reviewer will settle any discrepant readings.

6.10.2. Clinical Laboratory Studies

At enrollment and every 8 weeks during follow-up for pregnant women and every 16 weeks for children, venipuncture blood samples will be collected for routine clinical laboratory studies, including CBC and ALT measurements. Additional venipunctures will be performed, as appropriate, for laboratory testing to evaluate non-malarial medical illnesses at the discretion of study physicians. Results will be made available to study physicians in a timely manner for patient management decision-making. Additional hemoglobin measurements will be performed each time a patient is diagnosed with malaria using a portable spectrophotometer (HemoCue, Angholm, Sweden) and results will be immediately available.

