6.2. Diagnosis and Management of Malaria

Patients found to have malaria based on laboratory confirmation will have a second finger prick for a thin smear (to determine parasite species), hemoglobin measurement using a portable spectrophotometer (HemoCue), and collection of plasma for future PK studies. All episodes of malaria will be classified as uncomplicated or complicated based on the following criteria:

Uncomplicated malaria (all of the following)

- 1) Fever ($\geq 38.0^{\circ}\text{C}$ tympanic) or history of fever in the previous 24 hours
- 2) Positive thick blood smear
- 3) Absence of complicated malaria

Complicated malaria (any of the following)

- 1) Evidence of severe malaria (Appendix F) and parasitemia
- 2) Danger signs present in children (Appendix F) and parasitemia

Episodes of malaria will also be classified into the following categories according to the timing of previous malaria episodes for treatment purposes:

1. New episodes of malaria will be defined as any first episode or any episode occurring > 14 days after the diagnosis of a previous episode
2. Treatment failures will be defined as any of the following:
 - a. Complicated malaria occurring 1-14 days after the diagnosis of a previous episode
 - b. Fever ($\geq 38.0^{\circ}\text{C}$ tympanic) or history of fever in the previous 24 hours with a parasite density \geq the parasite density of an episode of malaria diagnosed 2 days prior

- c. Fever ($\geq 38.0^{\circ}\text{C}$ tympanic) or history of fever in the previous 24 hours with a parasite density $\geq 25\%$ of the parasite density of an episode of malaria diagnosed 3 days prior
- d. Fever ($\geq 38.0^{\circ}\text{C}$ tympanic) or history of fever in the previous 24 hours with a positive thick blood smear of any parasite density occurring 4-14 days after the diagnosis of a previous episode

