6.5. Routine Assessments

Routine assessments will be done in the clinic every 4 weeks for both pregnant women and children. Study participants not seen in the clinic for their every 4 week routine visits will be visited at home and requested to come to the study clinic as soon as possible. Pregnant women and children will receive standards of care as designated in the Uganda MOH guidelines (Appendix G). Routine antenatal care will include screening and treatment for sexually transmitted Infections, blood pressure assessment, urine dipstick for proteinuria, prescription of iron, folate, multivitamins and mebendazole. Routine care in children will include immunizations, vitamin A supplementation, and management of anemia using Integrated Management of Childhood Illness (IMCI) guidelines. During routine assessments subjects will be asked about visits to outside health facilities and the use of any medications outside the study protocol. The study protocol will be reinforced with discussion regarding the need to come to the study clinic promptly upon the onset of any illness and to avoid use of outside medications. Standardized assessment of adherence will also be done for study drugs administered at home and ITN use. A routine history and physical exam will be performed using a standardized clinical assessment form. Blood will be collected by finger prick (in very young children, heel sticks may be substituted for finger pricks) for thick smear, collection of plasma for PK studies, and filter paper samples. If a pregnant woman or parent/guardian of a child reports a fever in the last 24 hours or the patient has a documented temperature $\geq 38.0^{\circ}\text{C}$ tympanic, the patient's thick blood smear will be read immediately and if positive the patient will be diagnosed and treated for malaria (see section 6.2). Phlebotomy for routine laboratory tests (CBC and ALT) to monitor for potential adverse events from study medications and for immunology studies will be performed every 8 weeks in pregnant women and every 16 weeks in children. Screening for non-malaria parasitic infections will be performed once in pregnant women after the 1st trimester at the time routine mebendazole is administered and in children at 1 year of age.

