7.1.2. Identification of Adverse Events

At each scheduled and unscheduled visit to the clinic, study clinicians will assess patients according to a standardized case record form. A severity grading scale, based on toxicity grading scales developed by the NIH Divisions of AIDS (DAIDS) and the Division of Microbiology and Infectious Diseases (DMID) Pediatric Toxicity Tables, will be used to grade severity of all symptoms, physical exam findings, and laboratory results (Appendix J). All participants, regardless of treatment arm, will be assessed using the same standardized case record form. Adverse event monitoring will occur during the period when study drugs are given and up to 1 month after cessation of study drugs.

Data will be captured on the incidence of all adverse events, regardless of severity. For each adverse event identified and graded as severe or life threatening and felt to be possibly, probably or definitely related to study drugs, an adverse event report form will be completed. In addition, an adverse event form will be completed for all serious adverse events and unexpected events, regardless of severity. An adverse event report form will not be completed for events classified as mild or moderate (unless they are serious or unexpected), as mild and moderate symptoms are common and difficult to distinguish from signs and symptoms due to malaria and other common illnesses. The following information will be recorded for all adverse experiences that are reported:

- 1) Description of event
- 2) Date of event onset
- 3) Date event reported
- 4) Maximum severity of the event
- 5) Maximum suspected relationship of the event to study drugs (either SP or DP)

- 6) Whether the event is a serious adverse event
- 7) Initials of the person reporting the event
- 8) Outcome
- 9) Date event resolved

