8.1.3. Analyses

An intention-to-treat approach to all analyses will be used, including all study participants randomized to therapy and including all follow-up time until the study participants complete the study or early study termination regardless of whether the intervention was stopped due to an adverse event.

Primary analysis. We will compare the prevalence of placental malaria defined by histopathology at birth between the study arms using the Chi-Square test for all pair-wise comparisons. We will explore for any differences of potential confounders between the treatment arms and if necessary adjust our analysis using multivariate logistic regression.

Secondary analyses. We will compare the prevalence of placental parasitemia and our composite birth outcome using the Chi-Square test. We will compare the incidence of maternal malaria and adverse events using Poisson or negative binomial regression models. The Poisson models will include the logarithm of the follow-up time as an offset. We will translate the fitted coefficients and their confidence bounds into percentage effects with the formula $100 * [\exp(\text{coefficient}) - 1]$. This approach is closely related to exponential survival models for analyzing events per follow-up time, but is better able to adjust for violated assumptions. Testing for overdispersion in the Poisson regression can detect violations of these assumptions, and variances can be adjusted accordingly to produce valid p-values and confidence interval. If significant deviations from required distributions in study data are detected, we will employ negative-binomial or zero-inflated negative-binomial models to account for the observed pattern of data. We will compare the prevalence of maternal anemia and asymptomatic parasitemia using generalized estimating equations with adjustments for repeated measures in the same study participant. If necessary, multivariate analyses will be performed to adjust for potential confounders and effect modifiers.

8.2. Hypothesis 2

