8.2.2. Secondary Outcomes

Secondary outcomes are summarized in Table 8 below.

Table 8. Secondary outcomes

Secondary outcome	Definition
Incidence of complicated malaria	Any treatment for malaria meeting criteria for severe malaria or danger signs
Incidence of hospital admissions	Admission to the pediatric ward for any cause
Incidence of adverse event	Adverse events stratified by type, severity score and relationship to study drugs
Prevalence of anemia	Proportion of routine hemoglobin measurements < 10 g/dL & < 8 g/dL
Prevalence of asymptomatic parasitemia	Proportion of routine samples (PCR or blood smears) positive for asexual parasites.
Prevalence of gametocytemia	Proportion of routine blood smears positive for gametocytes.

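### In children, an extra haemoglobin test at each malaria diagnosis gives the arm with more malaria more chances to have anaemia counted; a routine-CBC-only comparison beside the planned one would separate the two

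*Protocol*

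**What the plan says.** Sections 6.5 and 6.10.2 set a fixed haemoglobin schedule that is the same in every arm: phlebotomy for CBC and ALT "will be performed every 8 weeks in pregnant women and every 16 weeks in children". Section 6.10.2 then adds tests that depend on malaria: "Additional hemoglobin measurements will be performed each time a patient is diagnosed with malaria using a portable spectrophotometer". Section 6.2 repeats this for every laboratory-confirmed episode.

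Section 7.1.2 has clinicians assess participants "At each scheduled and unscheduled visit to the clinic", with a severity scale that "will be used to grade severity of all symptoms, physical exam findings, and laboratory results". Haemoglobin has its own adult and paediatric grades in Appendix J. Nothing limits the grading to routine samples.

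For children, Table 8 defines the adverse event outcome as "Adverse events stratified by type, severity score and relationship to study drugs", so anaemia is a line of its own. Section 8.2.3 compares adverse event incidence with Poisson or negative binomial models and refers back for the method (its cross-reference reads 9.1.3; the description stands in 8.1.3). There, "The Poisson models will include the logarithm of the follow-up time as an offset". Section 8.5.2 builds its safety rate ratio from grade 3/4 events and SAEs.

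The separate anaemia prevalence outcome in Tables 7 and 8 is confined to routine haemoglobin measurements.

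**The concern.** A laboratory anaemia event can be recorded only when haemoglobin is measured. Here, part of the measuring is triggered by malaria, and hypothesis 2 expects malaria to differ between the infant arms. With follow-up time as the denominator, the anaemia rate ratio mixes two things: how often anaemia occurs and how often anyone looked.

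The direction is predictable. The arm with less malaria is tested less and so looks safer. In infants that arm is expected to be monthly DP, which is also the more heavily dosed one. A real haematological excess there could be partly hidden.

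Anaemia is not a marginal event type: in the group's earlier trial at this site it made up 56 of 169 grade 3-4 events (33%) in the control arm (Table 14). The protocol applies the safeguard of routine measurements only to anaemia prevalence, and not to adverse event incidence.

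**Working it through.** **Inputs**
- Routine CBC every 16 weeks in children (6.5, 6.10.2): 365.25/112 = 3.26 per year.
- One HemoCue test per malaria diagnosis (6.2, 6.10.2).
- Malaria rate r in the 3-monthly arm: 3 to 5 episodes per person-year (8.4, Table 10).
- Malaria reduction e with monthly DP: 20%, inside the 18-23% detectable range in 8.4; and 58% from Table 1. The 58% is monthly DP against no chemoprevention, so it is an assumption here.
- Mean anaemia spell μ of 2, 4 or 8 weeks. The protocol gives no duration; this is an assumption.

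**Plan's own figure.** No anaemia event rate is stated for this trial. The only one is in Table 14 for the earlier trial. It reproduces with one time denominator for different event types: 56/0.384 = 145.8 person-years for anaemia and 169/1.159 = 145.8 for all grade 3-4 events.

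**Step 1. Share of tests that depend on malaria, 3-monthly arm:** r/(r + 3.26).
- r = 3: 3/6.26 = 48%.
- r = 5: 5/8.26 = 61%.

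**Step 2. Tests per child-year, monthly over 3-monthly:** (3.26 + r(1 − e))/(3.26 + r).
- e = 20%: 5.66/6.26 = 0.90 (r = 3); 7.26/8.26 = 0.88 (r = 5).
- e = 58%: 4.52/6.26 = 0.72 (r = 3); 5.36/8.26 = 0.65 (r = 5).

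**Step 3. Effect on the anaemia rate ratio when true anaemia is equal.** Let spells be exponential with mean μ weeks, start at a random point in the 16-week cycle, be counted once, and be unrelated to malaria timing. With δ = 1/μ, λ = r/52.18 per week and s = δ + λ, the chance that a spell is detected is

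P = 1 − (δ/s) × [1 − (1 − exp(−16s))/(16s)].

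Example, μ = 4, r = 5, e = 58%:
- 3-monthly: δ = 0.25, λ = 0.0958, s = 0.3458, P = 1 − 0.7229 × 0.8200 = 0.407.
- Monthly (r = 2.1): λ = 0.0402, s = 0.2902, P = 1 − 0.8613 × 0.7867 = 0.322.
- Spurious rate ratio: 0.322/0.407 = 0.79.

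| Malaria, 3-monthly arm | Reduction | 2 weeks | 4 weeks | 8 weeks |
|---|---|---|---|---|
| 3 per year | 20% | 0.93 | 0.95 | 0.97 |
| 5 per year | 20% | 0.91 | 0.93 | 0.96 |
| 3 per year | 58% | 0.78 | 0.84 | 0.90 |
| 5 per year | 58% | 0.73 | 0.79 | 0.86 |

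The spurious reduction is therefore about 3-9% for a 20% malaria reduction and about 10-27% for 58%.

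**Step 4. Sensitivity to spell length.** At a mean of 16 weeks the ratios are 0.98 (20% reduction) and 0.92-0.94 (58%). If every spell lasted at least 16 weeks, routine testing would catch all of them and the ratio would be 1.00.

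**Step 5. Routine CBCs only.** Each arm is scheduled for 3.26 tests a year, so the testing ratio is 1.00 and this artefact disappears.

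**The case against.** **Size.** The 58% is not this trial's contrast, since every child here receives DP. Near the 18-23% difference in 8.4 the artefact is small. With fixed spells of 2 to 8 weeks, an assumed 0.6 true spells per child-year, 90 children per arm and 1.9 years each, a two-sided 5% test would reject in only about 6% of trials. This stands, and the larger figures must be read as conditional. But 18-23% is a detectable difference, not a forecast. Section 1.1 cites a trial in Thai adults with 98% efficacy for monthly and 86% for two-monthly DP, that is 2% against 14% of the placebo rate, a relative reduction of 1 − 2/14 = 86%. Population and interval differ, but a large effect of dosing interval is plausible.

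**Other routes to detection.** Physical examination at every visit, anaemia management at routine visits and discretionary venipuncture for other illness could all reveal anaemia and shrink the artefact. This stands; the calculation leaves them out.

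**Protection already there, and detail for the SAP.** Anaemia prevalence is restricted to routine samples, and how laboratory values become counted events is often left to the SAP, which is not at hand. In part this stands. Yet the protocol itself fixes which results are graded and the time denominator, and following it as written produces the link.

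**Stronger readings a reader might draw.**
- That an observed anaemia difference would be only a testing artefact. The documents do not support this: severe anaemia is a criterion of severe malaria in Appendix F, so part of any difference would be real.
- That sick-visit anaemia should leave the safety rate ratio in 8.5.2. That would remove true grade 3/4 events and SAEs from DSMB review, a worse trade.
- That the same bias size applies to women. They have 8-weekly CBCs and 8.4 assumes no maternal malaria incidence, so no size can be shown.

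**Conclusion.** The point holds as a cheap improvement, not as an error that invalidates a planned analysis. Under the protocol as written, the chance of detecting anaemia in children rises with malaria incidence, and the adverse event rate does not allow for it. The resulting spurious reduction in the anaemia rate ratio is about 3-9% if monthly DP cuts malaria by 20%, and about 10-27% if it cuts it by an assumed 58%.

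These figures assume equal true anaemia, mean spells of 2 to 8 weeks, detection only at routine CBCs and malaria visits, and no link in time between malaria and anaemia. They shrink for longer spells. The direction favours the lower-malaria arm. The parts affected are the anaemia adverse event line and, diluted by other event types, the grade 3/4 total and the safety rate ratio in 8.5.2. Anaemia prevalence in Tables 7 and 8 is untouched.

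**What to change.** - **Section 8.2.3, and by the same rule 8.1.3:** add a between-arm comparison of haemoglobin-based adverse events restricted to scheduled routine CBCs, as Tables 7 and 8 already do for anaemia prevalence. Tabulate the grades of malaria-day HemoCue values separately by arm.
- **Section 8.5.2:** keep the all-source rate ratio of grade 3/4 events and SAEs as defined, with every SAE and all sick-visit anaemia included. Show the DSMB the routine-only anaemia comparison beside it.

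Clinical care, individual event reporting and data collection do not change. The cost is a few sentences, a marker separating routine from malaria-day haemoglobin, and a little more analysis. The routine-only comparison will contain fewer events and so be less precise, which is why it should stand beside the all-source analysis and not replace it.

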6.10.3. Placental Studies

Cord blood will be collected for immunology studies described below. Placental blood collected for Giemsa-stained blood smears and PCR will be obtained by making a small incision on the maternal surface of the placenta within 1 hour of delivery, collecting blood from the intervillous space via syringe, and then placing the blood in an EDTA tube. Placental tissue will be collected for histological assessment. Two 1 cm-wide full thickness biopsies from each placenta, obtained about 5 cm from the cord, will be obtained within 1 hour of delivery and placed in 10% neutral buffered formalin. Biopsy specimens will be embedded in paraffin wax, sectioned into 3 μ M slices using a rotary microtome, fixed to glass slides, and dehydrated in sequential ethanol baths. Separate slides will then be stained in 0.1% hematoxylin and 1% eosin for 5 and 1 min, respectively, or in 2% Giemsa for 30 minutes. All necessary expertise and infrastructure for these studies is in place in Tororo. For assessment of histologic evidence of placental malaria, placentas will be graded into 5 categories using a standardized approach.⁸⁰ The presence of

intervillous parasite-infected erythrocytes and of pigment in monocyte/macrophages or fibrin will be noted. Quantitative assessments of placental malaria will be as follows. First, 1000 intervillous blood cells will be counted under high power. Percentages of intervillous erythrocytes infected with parasites and of monocyte/macrophages containing malarial pigment will be counted. Placental specimens will be examined by two experts, and any discrepant readings will be resolved by a third reader.

6.10.4. Molecular and Parasitology Studies

Each time a thick blood smear is obtained; blood will also be collected onto filter paper. Samples will be collected by venipuncture or by finger prick sampling. Blood will be placed onto filter paper in approximately 25 µl aliquots per blood spot (4 blood spots per sample). The samples will be labeled with study numbers and dates, air-dried, and stored in small, sealed sample bags at ambient temperature or 4°C with desiccant. Molecular studies will include the extraction of DNA from filter paper and followed by characterization of parasite genetic polymorphisms using standard molecular procedures including PCR, DNA hybridization, and/or restriction enzyme digestion. Additional molecular studies will include analyses of polymorphisms in parasite genes for mutations that may impact on malaria infection and response to antimalarial therapy. Molecular studies will be performed only for research purposes and will have no impact on the clinical management of study patients. Molecular studies will be formed in Uganda whenever possible and at UCSF when facilities/equipment are not available in Uganda.

Blood collected by venipuncture on the day malaria in child is diagnosed will be used in selected subjects for parasite culture and/or immunology studies (below). For these studies the skin will be prepped with 3 washes with a betadine or equivalent sterilizing solution, and then approximately 3-5 mls of blood in children <2 years of age, or 6-10 mls of blood in children ≥2 years of age will be collected in an anticoagulated sterile tubes and transferred promptly (generally within 30 minutes) to our molecular laboratory. Parasites will be cultured following standard protocols. In brief, erythrocytes will be separated from plasma by centrifugation and removal of the supernatant and buffy coat, and the infected erythrocytes will then be cultured in RPMI medium supplemented with human serum or Albumax serum substitute. Cultured parasites will be evaluated for in vitro drug sensitivity, molecular characteristics, and other features to characterize antimalarial drug resistance and other aspects of malaria. Information from the parasitology studies will have no impact on patient care.

6.10.5. Immunology Studies

Venipuncture blood samples collected at enrollment, during routine visits done every 8 weeks in pregnant women and every 16 weeks in children, and in select subjects on the day malaria is diagnosed (above) will be made available for immunology studies. Approximately 15mls of blood in pregnant women and 5mls of blood in children will be collected and separated into plasma and peripheral blood mononuclear cells (PBMC) using a Ficoll gradient, following standard protocols. Plasma will be stored at -80°C for future immunologic, which may include measurement of levels of cytokines, antibodies, and other features related to the host immune response. PBMCs will be stored in liquid nitrogen to maintain viability, and will be evaluated using flow cytometry, ELISPOT, RT-PCT, expression microarrays and other assays to assess the host immune response. Stool will be collected at 1, 2, and 3 years of age in children and evaluated for parasitic infections, and remaining stool will be stored for future studies analyzing the influence of parasitic and bacterial infections on immunity. Information from immunology studies will have no impact on patient care. Immunology studies will be done in Uganda whenever possible. However, due to technological limitations some immunology studies may be done at UCSF.

